
## Rationale

Though exercise treadmill test has high false positive and negative rates(Zang et al., 2007) , it is cheap, easily available, less time consuming to the interpret results and its accuracy can be increased by calculating ST/HR index, treadmill score, QT dispersion and so on (Kronander 2010 &Dentrano 1989). On the contrary the gold standard test coronary angiogram for detecting CAD is expensive, time consuming, potentially hazardous with many complications and often the CAG shows normal coronary arteries in female population. ST-segment depression and chest pain as the classic criteria for CAD diagnosis are well known and accepted. Besides If treadmill score were used the diagnostic accuracy of ETT would had been higher. The accuracy of different treadmill scores in Bangladeshi population especially the female population is largely unknown. Duke Treadmill Score and Simple Treadmill Score are well validated score in western population and are used for diagnostic & prognostic interpretation of ETT. The predictive accuracy of DTS to diagnose CAD is 71% (Fearon 2002). In 2001 Raxwal V et al. showed simple treadmill score has sensitivity of 88% and specificity of 96%. If we calculate the accuracy of simple treadmill score using the formula “Accuracy = (Sensitivity) x Prevalence + (Specificity) x (1- Prevalence)” it sums up nearly 93% according to prevalence of CAD in urban population. Cleveland Clinic Score is a prognostic score of ETT. It gives value from which we can predict the probability of 3 year or 5 year survival. It was shown that it has a very high negative predictive value approaching 97%. Besides to the best of our knowledge Cleveland Clinic Score was not tested as a diagnostic predictor of CAD and there are few studies regarding treadmill scores predictability in Bangladesh. In our study we will use all of these three scores and compare their accuracy to predict significant CAD. DTS, Simplified Treadmill Score, and Cleveland clinic score can be implemented effectively to identify patients with low probability of CAD and excluded from undergoing expensive and potentially hazardous CAG if the real scenario of the treadmill scores is known in our population.

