## **Procedures during study**

### **Exercise Treadmill Testing**

Patients will be undergoing treadmill testing using Bruce treadmill protocol. Before treadmill testing, the patients will be given a questionnaire. This questionnaire will estimate the patient's exercise capacity before the test and thus will allow most patients to reach maximal exercise capacity (Myers 1994). Visual ST-segment deviation will be measured at the J junction and will be corrected for pre-exercise ST-segment depression while standing; ST slope will be measured over the following 80 ms and will be classified as up sloping, horizontal, or down sloping. Slope will be coded as 1 horizontal, down sloping, or upsloping ST depression and 0 for normal slope (up sloping  $<2$  mm or ST-segment depression of  $<0.5$  mm). The ST response will be considered which has the most horizontal, downsloping or up sloping ST-segment depression in any lead, except aVR, during exercise or recovery. An abnormal response will be defined as  $\geq 1$  mm of horizontal or downsloping or  $\geq 2$  mm upsloping ST-segment depression (Griffin 2013). The exercise tests will be analyzed, and reported per standard protocol and manual calculation. Decision for cardiac catheterization will be consistent with clinical practice. Analyses will be performed with the investigators blinded to clinical and angiographic results.

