## Statistical Methods

Using angiographic evidence of CAD as the reference, area under the curve (AUC) of receiver operator characteristic (ROC) plots will be determined for the ST response alone and for each treadmill score. The AUC for each treadmill score will be compared with the AUC of the ST response alone and the AUCs of the other treadmill scores. A significant difference is defined as a z-score  $>1.96$ , with  $z\text{-score} = (AUC_1 - AUC_2) / (\text{SE}_1^2 + \text{SE}_2^2)^{1/2}$ . The predictive accuracies of the DTS, the Simple Treadmill Score and Cleveland Clinic Score to stratify patients into high or low likelihood for CAD will be calculated and compared. Test of agreement will be calculated using Kappa statistics. Statistically significant difference between predictive accuracies is defined as a p value  $<0.05$  using the two-tailed Fischer's exact test. Statistical analysis will be performed with the SPSS.

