## Appendix A

### Treadmill Scores and their calculation

The DTS will be calculated as  $DTS = \text{exercise time} - (5 \times \text{ST deviation}) - (4 \times \text{exercise angina})$ , with 0 = none, 1 = non-limiting, and 2 = exercise-limiting angina. The METs will be calculated by modified Bruce protocol and be inputted into the DTS equation (Fletcher et al., 1995). Based on the study by Shaw *et al.* (1998), a  $DTS < +5$  is considered abnormal. High risk when  $DTS < -10$  and low risk when  $DTS > +5$ .

The simple Treadmill Score for men will calculated as follows:

$(6 \times \text{maximal heart rate code}) + (5 \times \text{ST-segment depression code}) + (4 \times \text{age code}) + \text{angina pectoris code} + \text{hypercholesterolemia code} + \text{diabetes code} + \text{treadmill angina index code}$ .

The simplified score had a range from 6 to 95, with  $< 40$  designated as low probability, between 40 and 60 was intermediate probability, and  $> 60$  was high probability for CAD.

For male patient

Variable	Choose Response	Sum
Maximal HR	$<100 \text{ bpm} = 30$	
	$100-129 \text{ bpm} = 24$	
	$130-159 \text{ bpm} = 18$	
	$160-189 \text{ bpm} = 12$	
	$190-220 \text{ bpm} = 6$	
Exercise ST depression	$1 - 2 \text{ mm} = 15$	
	$>2 \text{ mm} = 25$	
Age	$>55 \text{ yr} = 20$	
	$40-55 \text{ yr} = 12$	
Angina history	Definite/typical = 5	
	Probable/atypical = 3	

[figure not shown]
	Non-cardiac pain = 1	
Hypercholesterolemia	Yes = 5	
Diabetes	Yes = 5	
Exercise test: induced angina	Occurred = 3	
	Reason for stopping = 5	
	Total score:	

For Female patients

Variable	Choose Response	Sum
Maximal HR	<100 bpm = 20	
	100-129 bpm = 16	
	130-159 bpm = 12	
	160-189 bpm = 8	
	190-220 bpm = 4	
Exercise ST depression	1 – 2 mm = 6	
	>2 mm = 10	
Age	>65yr = 25	
	50-65 yr = 15	
Angina History	Definite/typical = 10	
	Probable/atypical = 6	
	Non-cardiac pain = 2	
Smoking	Yes = 10	
Diabetes	Yes = 10	
Exercise test: Induced angina	Occurred = 9	
	Reason for stopping = 15	
Estrogen status	+ve = -5, -Ve = 5	
	Total =	

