**Fig: Cleveland Clinic Score Nomogram.**

## Appendix B

### Study design flow chart:

**Patient with Stable chest pain who underwent ETT and admitted for CAG**

**Patient selected according to Inclusion and exclusion criteria**

**DTS, Simple Treadmill Score, Cleveland Clinic score calculated**

**Report collection after CAG**

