### Coronary angiogram:

29. Extent of disease: 0= Normal, 1=SVD, 2=DVD, 3=TVD, 4=LM

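### The AUC comparisons use a z formula for independent samples although every patient has all the scores, so real differences are more likely to be missed

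*Combined protocol and SAP*

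**What the plan says.** The Statistical Methods section plans an ROC curve for the ST response and for each score, with angiographic CAD as the reference. "The AUC for each treadmill score will be compared with the AUC of the ST response alone", and the scores are also compared with one another. Four markers give six pairs: three scores against ST, and three score-against-score contrasts. The rule is the same for all: "A significant difference is defined as a z-score" greater than 1.96, where z is the AUC difference divided by the square root of the sum of the two squared standard errors.

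The rest of the protocol describes a paired design:

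- **Rationale:** "In our study we will use all of these three scores and compare their accuracy to predict significant CAD".
- **Appendix B flow chart:** a single stream of patients, with "DTS, Simple Treadmill Score, Cleveland Clinic score calculated" before the angiogram report is collected.
- **Appendix C form:** one form per patient holds ST depression, DTS, STS and CCS, followed by one angiographic result: "Extent of disease: 0= Normal, 1=SVD, 2=DVD, 3=TVD, 4=LM".

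No section names a paired ROC method. The dummy AUC table has a standard error and interval for each score and a test against 0.5. It has no row or column for a difference between two AUCs.

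**The concern.** For two AUCs estimated in the same patients, the variance of the difference is SE1² + SE2² − 2·r·SE1·SE2, where r is the correlation between the two estimates. The plan drops the last term. Positive r is to be expected once the scores are oriented the same way. The patients and the reference result are shared. By Appendix A, DTS and STS both use ST depression and exercise angina, and the ST comparator is itself a component of both. The inputs to CCS are not visible in the text, but pairing by patient applies to it as well.

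The general objective is to identify how the scores differ in predicting significant CAD, and the AUC test is one of two planned comparisons for it. If the standard error is too large, a real difference is more likely to come out non-significant and be read as showing that the scores are interchangeable. That matters because the Rationale intends the scores to identify patients who could be spared angiography.

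**Working it through.** **The plan's own figure.** The Sample size calculation uses p1 = 0.71, p = 0.55, Zα = 1.96 and Zβ = 1.28:

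[1.28·√(0.55×0.45) + 1.96·√(0.71×0.29)]² / 0.16² = (0.637 + 0.889)² / 0.0256 ≈ 90.98, i.e. 91.

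Allowing for 10% non-response, 91/0.9 = 101.1, i.e. 102. The figure reproduces, but it concerns a single predictive accuracy. The plan states no power for an AUC difference.

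**Inputs for the AUC test**

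- From the plan: N = 102 (91 before non-response), and an AUC of 0.83 for DTS, quoted in the Literature Review.
- Assumed: 60% with CAD (61 with, 41 without), a comparator AUC of 0.73, r from 0 to 0.7, and the rule read as |z| > 1.96.

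**Standard errors (Hanley–McNeil).** With Q1 = A/(2 − A) and Q2 = 2A²/(1 + A),

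SE² = [A(1 − A) + (n1 − 1)(Q1 − A²) + (n0 − 1)(Q2 − A²)] / (n1·n0).

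This gives 0.0396 for A = 0.83 and 0.0491 for A = 0.73.

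**SE of the difference.** As planned, √(0.0396² + 0.0491²) = 0.0631 at any r, so an observed difference must exceed 1.96 × 0.0631 = 0.124. Paired at r = 0.5, √(0.0631² − 2×0.5×0.0396×0.0491) = 0.0451, so the threshold is 0.088.

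**Power.** The true sampling SD of the difference is the paired SE. At r = 0.5:

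- Planned rule: Φ[(0.10 − 0.1237)/0.0451] = Φ(−0.53) ≈ 30%.
- Paired rule: Φ(0.10/0.0451 − 1.96) = Φ(0.26) ≈ 60%.

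**Type I error of the planned rule** with equal AUCs: 2·P(Z > 1.96/√(1 − r)).

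| r | Paired SE | Paired threshold | Power, planned | Power, paired | Type I error, planned | N for 80% power, planned / paired |
|---|---|---|---|---|---|---|
| 0 | 0.0631 | 0.124 | 35% | 35% | 5.0% | not computed |
| 0.3 | 0.0531 | 0.104 | 33% | 47% | 1.9% | 287 / 224 |
| 0.5 | 0.0451 | 0.088 | 30% | 60% | 0.56% | 265 / 163 |
| 0.7 | 0.0355 | 0.070 | 25% | 80% | 0.035% | 239 / 101 |

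**Sensitivity to the assumptions**

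- Low correlation: 34.6% planned against 38.5% paired at r = 0.1, and 34% against 42% at r = 0.2.
- N = 91 with 50–70% CAD, at r = 0.3 / 0.5 / 0.7: 28–29 / 24–26 / 19–20% planned against 41–43 / 53–55 / 73–76% paired.
- Larger difference, 0.83 against 0.63, N = 102: 88 / 91 / 95% planned against 94 / 98 / >99% paired.
- ST response used as normal or abnormal. The Exercise Treadmill Testing section gives a cut-point ("An abnormal response will be defined as" a stated depth of ST depression), and the plan does not say which form enters the ROC analysis. With sensitivity 68% and specificity 77% from the Introduction, its AUC is (0.68 + 0.77)/2 = 0.725. Simulated against a score with AUC 0.83, power is 41 / 39 / 37% planned and 52 / 61 / 76% paired at r of about 0.24 / 0.40 / 0.58.

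**Simulation check.** In 4,000 paired binormal datasets per setting (61 with CAD, 41 without, DeLong variances), at r of about 0.30 / 0.49 / 0.70, power for 0.83 against 0.73 was 31 / 27 / 21% planned and 45 / 57 / 79% paired. With both AUCs at 0.78, type I error was 1.7 / 0.8 / 0.05% planned and 5.0 / 4.6 / 4.7% paired.

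**The case against.** The strongest reply is that the error is conservative and can be repaired late. It changes no point estimate, enrolment or data capture, and a paired test could be run on the recorded data at any time. The specific objectives and the sample size are worded in terms of accuracy rather than AUC. This is true, but the accuracy comparison is no safeguard: it uses Fisher's exact test, which also ignores the pairing. A rule that is wrong for the design should be corrected before the analysis.

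Second, the magnitude rests on assumptions. That stands. The only Bangladeshi angiographic figure in the protocol is 77.9%, a positive predictive value among ETT-positive patients. With 78% CAD and N = 102, power is 27 / 24 / 19% planned against 41 / 52 / 72% paired at r = 0.3 / 0.5 / 0.7: the same pattern, with a smaller gain.

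Third, six unadjusted tests raise multiplicity. With four equal AUCs and a common r, six paired tests carry a familywise error of about 20% at any r. The planned rule gives 20 / 8.8 / 2.9 / 0.2% at r = 0 / 0.3 / 0.5 / 0.7. So the conservatism holds for each comparison taken singly, not for the set, and part of the power gain comes from leaving an accidentally strict threshold. This is a separate matter and does not make the formula valid.

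Fourth, the fix does not rescue small contrasts. For 0.83 against 0.78 (N = 102, 60% CAD), paired power is only 17 / 22 / 33%. That also stands: N was not chosen for AUC differences.

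**Conclusion.** The concern holds and should be corrected before analysis. The stated rule omits the covariance between AUCs estimated in the same patients, and nothing elsewhere in the protocol supplies it. With equal standard errors, the SE of the difference is too large by a factor of 1/√(1 − r): 1.20, 1.41 and 1.83 at r = 0.3, 0.5 and 0.7.

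That the formula does not fit the design is certain from the text. The direction of the harm depends on positive r, which the shared patients and components make likely. Its size is illustrative, because r, the CAD share and the comparator AUC are all assumed. The loss is nil at r = 0, slight at 0.1, and large for a 0.10 difference at moderate or high r. A single difference declared significant under the planned rule is not undermined by this error; a non-significant one cannot be taken at face value.

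**What to change.** In Statistical Methods, replace the formula with a paired comparison of correlated ROC curves: either DeLong's test, or z = (AUC1 − AUC2)/√(SE1² + SE2² − 2·r·SE1·SE2) with r estimated from the data. State the rule as |z| > 1.96, since the text literally requires z itself to exceed 1.96. Orient all scores the same way first, because a low DTS is the abnormal direction. Report each AUC difference with its paired 95% confidence interval, and add those rows to the dummy AUC table. State that a non-significant result at N = 102 is not evidence that two scores are equivalent. While editing the passage, it would be sensible also to say how the six comparisons are to be interpreted together.

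The cost is one or two lines of text plus the table rows. If the SPSS version in use has no paired ROC comparison, this step can be run in another package. No extra patients or data are needed.

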### DTS \* CAD

#### Crosstab Count

	CAD		Total
	No CAD	NCAD	
Low likelihood			
High Likelihood			
Total			

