### Cleveland Clinic Score:(Lauer et al., 2007)

Arbitrarily, we assume CCS will predict significant CAD with high probability if the value is  $> 140$  and low probability if the value is  $< 100$ .

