### Exercise test variables:

18. Duration of exercise: .....min

19. METs .....

20. Maximum Heart Rate: .....bpm

21. Peak Systolic BP: .....mmHg

22. Maximum ST segment depression: .....mm

23. Exercise induced angina: 0= No angina 1= Non-test limiting

2= Test limiting angina

24. Abnormal heart rate recovery: 0= No 1= Yes

25. Frequent VE during recovery: 0= No 1= Yes

26. Duke Treadmill Score: ..... 0= Low risk

1= High risk

27. Simple Treadmill Score: ..... 0=Low probability

1=High probability

28. Cleveland Clinic Score: ..... 0=Low probability

1= High probability

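### The accuracy analysis needs every patient in a low or a high class, but the written cuts for the Simple Treadmill Score and the Cleveland Clinic Score do not provide this, and the Duke cut does not match its form labels.

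*Combined protocol and SAP*

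**What the plan says.** **Two classes are required.** Statistical Methods says that the predictive accuracies of DTS, STS and CCS "to stratify patients into high or low likelihood for CAD will be calculated and compared", with kappa for agreement and Fisher's exact test for differences. Each score's crosstab in Dummy Tables/Graphs has one low row and one "High Likelihood" row. The STS crosstab is a single table for both sexes. Items 26 to 28 of the data form (Appendix C) have codes 0 and 1 only, for example "0=Low probability". DTS is coded low risk or high risk.

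**The cuts are in Appendix A.**
- STS: a score below 40 is "designated as low probability, between 40 and 60 was intermediate probability, and" a score above 60 is high. These cuts follow the formula for men and come with this statement: "The simplified score had a range from 6 to 95". The women's table gives item points but no cut.
- CCS: "Arbitrarily, we assume CCS will predict significant CAD with high probability if the value is" above 140, and low if it is below 100. Nothing is said about 100 to 140.
- DTS: a score below +5 "is considered abnormal. High risk when" it is below -10, and low risk when it is above +5.

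No section excludes middle scores or says which class they join.

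**The concern.** Two readings are open. If the cuts are applied as written, patients in a middle zone have no cell. Each score then loses a different set of patients, so a difference in accuracy partly reflects who was left out. Leaving out the least certain patients also tends to raise accuracy. If everyone is instead forced into a class, the result depends on a choice that is not written down.

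Accuracy is named in Specific Objectives 1 and 2, and DTS accuracy (71%) is the quantity in the sample size calculation. No section calls it primary. The kappa and Fisher analyses use the same two classes.

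**Working it through.** **1. Which score do the STS cuts belong to?** Summing the largest item points in Appendix A:
- Men: 30 + 25 + 20 + 5 + 5 + 5 + 5 = 95. The lowest heart-rate item alone gives 6. This reproduces the stated range of 6 to 95.
- Women: 20 + 10 + 25 + 10 + 10 + 10 + 15 + 5 = 105.

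The stated range, and the cuts given with it, therefore fit the men's score only.

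**2. Which scores have no class?**

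| Score | Low | High | Left over |
|---|---|---|---|
| STS, men | < 40 | > 60 | 40 to 60 (labelled intermediate) |
| STS, women | not stated | not stated | all |
| CCS | < 100 | > 140 | 100 to 140 (no label) |
| DTS, form labels | > +5 | < -10 | -10 to +5 |
| DTS, abnormal or not | > +5 | < +5 | exactly +5 |

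**3. STS illustration.** The inputs are the women's validation counts in the Literature Review (CAD/total): 0/5, 3/26, 20/56, 33/81, 24/49, 22/32 and 7/7. Two assumptions are needed: that cuts of 40 and 60 apply to women, and that a score of exactly 60 counts as high. The published bands force the second, because they place 60 in the 60-69 group.
- Below 40: 5 + 26 + 56 = 87, of whom 23 have CAD.
- 40 to 59: 81 + 49 = 130, of whom 57 have CAD.
- 60 and over: 32 + 7 = 39, of whom 29 have CAD.
- Total: 256, with 109 CAD. The middle share is 130/256 = 51%.

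Accuracy = (TP + TN)/n, and kappa = (observed - expected agreement)/(1 - expected agreement).

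| Middle group | TP | FP | FN | TN | Accuracy | Kappa |
|---|---|---|---|---|---|---|
| Dropped | 29 | 10 | 23 | 64 | 93/126 = 73.8% | 0.44 |
| Counted low | 29 | 10 | 80 | 137 | 166/256 = 64.8% | 0.22 |
| Counted high | 86 | 83 | 23 | 64 | 150/256 = 58.6% | 0.21 |

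The spread is 73.8 - 58.6 = 15.2 points, or 64.8 - 58.6 = 6.2 points if everyone is classified. Sensitivity is 29/109 = 27% with the middle counted low and 86/109 = 79% with it counted high. Specificity is 137/147 = 93% and 64/147 = 44%.

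**4. DTS illustration.** This rests on an assumed binormal model.
- Separation: the 74% sensitivity and 73% specificity in the Literature Review give z(0.74) + z(0.73) = 1.26 SD. The implied AUC is 0.81, against 0.83 reported there.
- SD: assumed to be 5, 6 or 7, equal in both groups. The documents give no SD.
- Centres and prevalence: women 1.6 and 32%, men -0.3 and 72%, from the catheterization series in the Literature Review. Its averages are taken as means.
- Mix: 976 women and 2,249 men, from the same series.

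With prevalence p, overall mean m and distance D = 1.26 x SD, the CAD mean is m - (1 - p)D and the no-CAD mean is m + pD. Scores below the cut count as test-positive.

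| Group | Split at +5, all classified | Middle (-10 to +5) dropped |
|---|---|---|
| Both sexes | 72-73% | 79-81%, with 25-39 of 102 patients kept |
| Women | 57-61% | 90-93% |
| Men | 78-79% | 73-74% |

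**5. What cannot be sized.** The documents give no distribution for CCS, and none for STS in men.

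**The case against.** **The DTS rule is nearly complete.** Calling everything below +5 abnormal is almost a binary rule. This stands. What remains is the mismatch with the risk labels in item 26 and the score of exactly +5. A reader might go further and compare a split at +5 with a split at -10 that codes everything from -10 upward as low. Appendix A does not support that second split: low risk is above +5, and everything below +5 is abnormal.

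**The figures are borrowed.** This also stands. The STS counts apply to women a cut that the protocol never states for them, and the DTS model rests on an assumed SD and another series' sex mix. They show that the choice can matter, not what this study will find.

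**The coding is protected from the angiogram.** A reader might infer that classes could be chosen after the results are known. The documents do not show this. The exercise-test section says: "Analyses will be performed with the investigators blinded to clinical and angiographic results". The flow chart in Appendix B calculates the scores before the angiography report is collected, and items 26 to 28 come before the angiogram item. These safeguards count, but none of them fixes a cut, and the blinding sentence does not clearly cover the low/high coding.

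**Leaving out a middle group can be legitimate.** A pre-specified exclusion with the excluded share reported would remove the ambiguity. Unless all scores used one common subset, they would still be compared on different patients. An intermediate band may also serve Specific Objective 3, which relates score levels to severity, but that does not give it a place in a two-class table.

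**Conclusion.** The point holds and should be fixed. For STS and CCS the written cuts leave a middle zone outside the planned tables, and women have no stated STS cut although their results go into the pooled STS table. For DTS it is a matter of reconciling labels and one boundary value.

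In the one set of counts the protocol supplies, the handling of the middle group moves accuracy by up to 15 points. The sample size calculation is built on 71 - 55 = 16 points. The 15-point figure is conditional on cuts of 40 and 60 applying to women. In the DTS model, dropping the middle raises pooled accuracy by about 6 to 9 points and leaves well under half of the 102 patients.

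Two wider conclusions are not supported. Dropping the middle does not always inflate accuracy: in the model it lowers it in men. Nor is the whole analysis at risk: the AUC comparison uses the scores without classes and is unaffected.

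**What to change.** Without reference to the angiographic results:
1. Fix one binary analysis cut per score that classifies every patient. The choice is the study team's.
2. Reconcile the DTS cut in Appendix A with the labels in item 26 and the DTS crosstab, including a score of exactly +5.
3. State the STS cut for women.
4. Compare all scores on the same patients.
5. Report the intermediate share for each score, with sensitivity and specificity beside accuracy.
6. State that the blinding covers this coding. If angiographic results had already been seen when a cut was fixed, say so and show accuracy under each written reading.

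**Cost.** The change affects wording in Statistical Methods and Appendix A, and labels in the three crosstabs and items 26 to 28. No new data are needed, because those items already record the raw scores. Reported accuracies will usually be lower than with the middle left out. Row labels must make clear that intermediate patients are included. Comparison with the 71% in the sample size section may be less direct if that figure left out a middle group, which the documents do not show.

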## Literature Review

According to Islam AKMM and Majumder AAS “Coronary artery disease in Bangladesh: A review published in 2013 the exact prevalence of CAD in Bangladesh is not known. Only a limited number of small-scale epidemiological studies are available. Probably the prevalence of IHD was first reported in 1976, which was 0.33%. More recent data indicates CAD prevalence between 1.85% and 3.4% in rural and 19.6% in an urban sample of working professionals. Despite marked disparity in values, there seems to be a rising prevalence of CAD in Bangladesh.

Gianrossi et al. investigated the diagnostic accuracy of ETT through a meta-analysis including 147 published reports involving 24,074 patients who underwent both coronary angiography and ETT. There was a wide variability in sensitivity and specificity of ETT [sensitivity  $68 \pm 16\%$  (range 23–100%); specificity  $77 \pm 17\%$  (range: 17–100%)]. Another Meta analysis showed sensitivity of  $81 \pm 12\%$  (range: 40–100%) and specificity of  $66 \pm 16\%$  (range: 17–100%).

2014 Taimur et al evaluated ETT (Treadmill) Positive Patients in a Tertiary Care Hospital of Bangladesh by doing angiogram subsequently. They found the overall positive predictive value of ETT is 77.9%, and for male patient PPV is 86.25% and for female patient it is 50%.

In 1987 Mark DB et al showed Duke Treadmill Score was useful for stratifying prognosis in patients with suspected coronary artery disease who were referred for catheterization, and may provide a useful adjunct to clinical decision making in the larger population of patients being evaluated for chest pain. They had evaluated 2842 patients with chest pain who had both treadmill testing and cardiac catheterization.

Shaw LJ et al in 1998 estimated DTS provides accurate diagnostic and prognostic information for the evaluation of symptomatic patients evaluated for clinically suspected ischemic heart disease.

In 2015 Gunaydin et al showed there was a strong negative correlation between DTS and Syntax Score ( $r = -0.72$ ,  $p < 0.001$ ). The area under the receiver-operating curve of DTS was 0.83 (0.77-0.88,  $P < 0.001$ ) for predicting significant presence of CAD. The optimal cut-off value of DTS to predict the significant presence of CAD was -3.7 (sensitivity of

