## Sample size calculation

Sample size is calculated by using the following equation (One sample comparison of proportion):

$$n = \frac{[Z\beta\sqrt{p(1-p)} + Z\alpha\sqrt{p_1(1-p_1)}]^2}{(p-p_1)^2}$$

n = required sample size

p = Proportion under alternative hypothesis that is proposed to be detected or worst possible outcome

p1= Proportion under null hypothesis or proportion in the population

Z $\alpha$  = 1.96 (5% level of significance)

Z $\beta$  = 1.28 when power is 0.9

According to Fearon WF et al (2002) the predictive accuracy of DTS is 71% (0.71).

If we assume: p1= 0.71

P = 0.55, Power = 0.8,  $\alpha$  = 0.05

$$\begin{aligned} \text{Sample size} &= \frac{[1.28\sqrt{.55(1-.55)} + 1.96\sqrt{.71(1-.71)}]^2}{(.55 - .71)^2} \\ &= 91 \end{aligned}$$

Correction for non-response:

Nf= 100/100- Nr

If Nr= Percentage of expected non-response is 10%

Nf= 100/100- 10 = 1.11

[figure not shown]
Final sample size will be estimated sample size (n) x Nf

= 91 x 1.11 = 102. So our required sample size is at least 102.

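### At the high/low cut-off the scores are compared only on overall accuracy, with kappa alongside; sensitivity, specificity and NPV are not named results, so the plan does not show how well a low score rules out CAD

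*Combined protocol and SAP*

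**What the plan says.** Statistical Methods plans three things.

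- **AUC.** "The AUC for each treadmill score will be compared with the AUC of the ST response alone" and with the AUCs of the other scores.
- **Accuracy at the cut-off.** The predictive accuracies of the three scores "to stratify patients into high or low likelihood for CAD will be calculated and compared", with significance judged at p < 0.05 "using the two-tailed Fischer's exact test".
- **Kappa.** "Test of agreement will be calculated using Kappa statistics". The dummy tables place it under each score-by-CAD crosstab, so it measures agreement with angiography. No test between kappas is set.

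The dummy tables hold an AUC table with 95% intervals and, for each score, a two-by-two count table, chi-square and Fisher tests, and kappa. Sensitivity, specificity and predictive values are not named as results in the objectives, Statistical Methods or the dummy tables. They appear only where published work is described.

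The Rationale says the scores "can be implemented effectively to identify patients with low probability of CAD and excluded from undergoing expensive and potentially hazardous CAG". The abstract gives the same motive: fewer unnecessary angiograms. The formal objectives are worded differently: they speak of predictability, and of estimating and comparing accuracy.

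**The concern.** A patient classed as low would, under the Rationale, be spared angiography. The costly error is then a CAD patient classed as low. Sensitivity counts that error among CAD patients, and NPV counts it among those called low.

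Overall accuracy adds this error to the opposite one (a patient without CAD called high) and weights the two by prevalence. Two scores can therefore tie on accuracy while one misses several times as many CAD patients, and a test on accuracy has nothing to find. Kappa corrects for chance, but it also blends the two errors and can rank the scores in the wrong order for ruling out disease. AUC summarises all thresholds and does not describe the cut-off actually used.

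At stake is whether the report can support the use the Rationale proposes.

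**Working it through.** **Inputs.** n = 102 and the 71% accuracy are from Sample size calculation. The accuracy formula is the protocol's own (Rationale): accuracy = sensitivity × prevalence + specificity × (1 − prevalence). Prevalence proxies are from the Literature Review: 32% of women and 72% of men in a series with treadmill testing and catheterisation; 77.9% overall, 86.25% of men and 50% of women among ETT-positive patients in a Bangladeshi hospital. The 60% prevalence and the two sensitivity/specificity pairs in steps 2 and 3 are assumptions for illustration.

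**1. The plan's own use of the formula.** The Rationale takes sensitivity 88% and specificity 96% and reports nearly 93% accuracy at urban prevalence. At the 19.6% urban figure in the Literature Review, 0.88 × 0.196 + 0.96 × 0.804 = 94.4%. A result of 93% needs a prevalence of (0.96 − 0.93)/(0.96 − 0.88) = 37.5%. At 77.9% the same test gives 89.8%. The accuracy of a fixed test moves with prevalence.

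**2. Two scores tied on accuracy.** Prevalence 60%, so about 61 of 102 have CAD.

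| | Score A | Score B |
|---|---|---|
| Sensitivity / specificity | 90% / 42.5% | 65% / 80% |
| Accuracy | 0.54 + 0.17 = 0.71 | 0.39 + 0.32 = 0.71 |
| CAD patients missed | 0.10 × 61 ≈ 6 | 0.35 × 61 ≈ 21 |
| NPV | 0.17/(0.17 + 0.06) = 74% | 0.32/(0.32 + 0.21) = 60% |
| Called high | 0.54 + 0.23 = 0.77 | 0.39 + 0.08 = 0.47 |
| Chance agreement | 0.77 × 0.6 + 0.23 × 0.4 = 0.554 | 0.47 × 0.6 + 0.53 × 0.4 = 0.494 |
| Kappa | (0.71 − 0.554)/0.446 = 0.35 | (0.71 − 0.494)/0.506 = 0.43 |

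Accuracy shows no difference. Kappa favours B, which misses more than three times as many CAD patients.

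**3. What each test would see.** In whole patients (61 with CAD, 41 without), A is right in 55 + 17 = 72 and B in 40 + 33 = 73. Fisher's exact test of 72/102 against 73/102 gives p = 1.0. For sensitivity, A misses 6 and B misses 21. The discordant pairs then lie between 15 v 0 (A's misses all among B's) and 21 v 6 (no overlap). Exact McNemar p is 0.00006 and 0.006 respectively. The difference in sensitivity is found whatever the overlap.

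**4. A rule with no information.** Calling everyone high has accuracy equal to prevalence: 32% or 50% with the proxies for women, 72% to 86.25% with those for men. Its kappa is 0 and its AUC 0.5. At 77.9% its accuracy exceeds the 0.74 × 0.779 + 0.73 × 0.221 = 73.8% of a score with sensitivity 74% and specificity 73% (a DTS cut-off cited in the Literature Review). That score's kappa there is 0.38.

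**5. Prevalence dependence of kappa and NPV.** With sensitivity 80% and specificity 70% held fixed, kappa is 0.50, 0.44 and 0.30 at 50%, 77.9% and 90% prevalence (the 90% is assumed). With 74% and 73% held fixed, NPV is 85.6% at 32% prevalence, 44.3% at 77.9% and 30.9% at 86.25%. NPV therefore needs the prevalence printed beside it.

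**The case against.** The strongest defence is that comparing accuracy is what the specific objectives ask for, that ruling out CAD is rationale and not objective, and that the planned crosstabs already hold the counts for sensitivity, specificity and NPV. All three statements are correct. They make this a gap in the named and compared results, not in the data collected on the scores. They do not remove it: a quantity that could be worked out later is not a pre-specified comparison. The separate score-by-CAD tables also do not show the pairing between scores that such a comparison needs.

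Four stronger readings are tempting, and the documents do not support them.

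- *That calling everyone high would look good on the plan's measures.* This applies to accuracy only. Kappa is 0 and AUC 0.5 for such a rule, and the plan reports both.
- *That the cohort has high prevalence.* Enrolling patients already admitted for angiography makes this plausible, but no expected prevalence is stated and the proxies start at 32%. The 77.9% is a predictive value among ETT-positive patients, and a positive ETT is not an entry criterion here.
- *That 71% is a benchmark which an uninformative rule could beat.* It is the null proportion in the sample size formula, set against a lower alternative of 0.55. Nothing makes exceeding it a success criterion.
- *That accuracy is the sole comparison.* The pairwise AUC comparisons come first in Statistical Methods and are sound in aim. They leave open only what happens at the cut-off.

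**Conclusion.** The point holds as a gap in the planned results. At the cut-off, the scores are compared on a prevalence-weighted mix of two errors, and the error that matters for the Rationale is neither named nor tested. In the worked example, scores with identical 71% accuracy miss about 6 and 21 of 61 CAD patients, and kappa points to the wrong one for ruling out disease.

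The 6 v 21 contrast rests on an assumed 60% prevalence and on chosen sensitivities and specificities. It shows what the planned comparison could hide, and does not predict the study's result. The masking itself does not depend on high prevalence; the weakness of accuracy against an all-high rule does. The change is worth making before analysis. It does not call the design into question.

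**What to change.** In Statistical Methods and the dummy tables:

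1. For each score and for ST response, report sensitivity, specificity and the NPV of the low class, with exact 95% confidence intervals, beside the cohort's CAD prevalence.
2. Compare scores pairwise on sensitivity with McNemar's test in patients with CAD, and on specificity with McNemar's test in patients without CAD. Give NPV with its interval; McNemar's test does not apply to it.
3. Keep the AUC comparisons. Keep overall accuracy and kappa as supporting results.
4. State how values between the low and high limits enter the two-class tables. Appendix A leaves Simple Treadmill Score 40 to 60 and Cleveland Clinic Score 100 to 140 in neither class, and gives the DTS both a single abnormal limit and separate low and high limits. The low class must be defined before its NPV means anything.

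**Cost.** For the scores, no new data: the data collection form records each score and the angiographic result per patient. The additions are wording, a paired score-by-score table within each CAD group, and a crosstab for ST response, which the dummy tables lack. The form as printed records the depth of ST depression but has no field for slope, which the protocol's definition of an abnormal ST response uses; that field may need adding.

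The statistical price is wider intervals, because each measure uses part of the 102 patients. In the example, accuracy of 72/102 has an exact 95% interval of 61% to 79%, specificity of 17/41 one of 26% to 58%, and NPV of 17/23 one of 52% to 90%. That imprecision is real, and the report should show it.
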